Online Platform for Healthy Weight Loss (POEmaS)

February 9th, 2018

DATA ANALYSIS PLAN

Analysis will be on an intention-to-treat basis. Outcomes will be analyzed at two timepoints (12 and 24 weeks). Analysis of covariance will be used to test for differences in weight loss between groups at each time point. The models will be fitted using linear regression with weight as the outcome variable, treatment group as the predictor variable of interest and weight at baseline included as a covariate. Age, gender, dietary intake (kilocalories) and physical activity at baseline will enter the model for adjustment. Statistical significance of the primary efficacy analysis (at 12 and 24 weeks) will be based on Hochberg's multiple testing procedure with the family wise error rate for each time point held at 2.5%. Secondary hypothesis tests will be performed using a 2-sided 5% significance level.

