Online Platform for Healthy Weight Loss (POEmoS)

February 9th, 2018

STUDY PROTOCOL

Design

This is a three-arm parallel randomized controlled trial which recruited adults (18-60 years) participants classified as overweight or obese (body mass index – BMI ≥ 25 kg/m²) and who had the intention to lose weight.

Participants and recruitment

Students (current and past) and staff of the Federal University of Minas Gerais (UFMG), Belo Horizonte, in the southern Brazil, were recruited by physical and online advertising (flyers, University website, UFMG mailing list) for one month from the 25th September to 24th October, 2017. They were invited to access the project website www.poemasufmg.com.br, where they can watch a video with details of the project. Interested participants can join the project online and create an account profile after checking for the inclusion and exclusion criteria (Table 1) and signing the informed consent form. Participants excluded from the study can reference colleagues by entering their email.

Table 1- Inclusion and exclusion criteria for recruitment into “POEmas (Online Platform for healthy weight loss)” Randomized Clinical Trial

Inclusion criteria	Exclusion criteria
Age between 18 and 60 years	Pregnancy
BMI* ≥ 25 kg/m ²	Self-report of comorbidities that demand specific dietary or physical activity recommendations- diabetes, heart failure, coronary artery disease, kidney disease, hepatic disease, cancer, phenylketonuria, celiac disease, food allergies, bariatric surgery history
Intention to lose weight by changes in	Participation in any other weight loss

lifestyle habits	program
Internet access	

* BMI: Body mass index

Randomization and allocation

Once informed consent was obtained, participants were randomly allocated to one of the three groups using a stratified randomized block design. Participants were stratified by gender and category of body mass index (25 to <30 or ≥ 30 kg/m²) using blocks of variable length (either 3 or 6).

Participants were initially allocated to one of three groups:

- (1) Group 1, control group which is submitted to an initial minimal intervention for 24 weeks and subsequently will have access to all the platform functionalities;
- (2) Group 2 will follow a standard weight loss program delivered by the website platform for 24 weeks;

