- (3) Group 3 followed the standard weight loss program enhanced by personalized feedback by a nutritionist based on lifestyle habits reported in the platform for 12 weeks and the standard weight loss program for the following 12 weeks.

Subsequently, subjects received an automatic email with detailed information on the groups they were allocated to. Researchers were blinded to participants' allocation.

Outcome measures

All outcomes will be assessed at baseline, 12 and 24 weeks afterwards. Weight and BMI change are the primary outcomes of the study and will be self-reported by the participants. Secondary outcomes will be changes in dietary habits, food-related behaviors, physical activity habits, sedentary behaviors, quality of life, health perception, online activity and users' satisfaction, as detailed in Table 2. Outcome assessors will be blinded to group allocation.

Sample size

Based on a 90% power to detect a significant difference of 4kg weight loss between groups, assuming the SD of weight is 6.0 and using a two-sided significance level of 0.05, and a 40% attrition rate, a sample size of 90 participants was calculated for each group.

Interventions

The interventions will be delivered online for 24 weeks, with new program content distributed to the user weekly for Groups 2 and 3. The content of dietary and physical activity recommendations was based on Brazilian and international evidence-based guidelines. Dietary recommendations focused on particular Brazilian habits. Physical activity recommendations focused on increasing time of leisure exercise and decreasing sitting time.

In group 1, subjects have access to four videos with information on health consequences of excessive weight, dietary and physical activity weight loss recommendations, as well as strategies to behavior change. They also received an e-book with lifestyle habits and behavioral recommendations to lose weight. Access to the study website will be limited for the first 24 weeks and they have been asked not to undertake any other weight-loss program during this time. They will be invited to report their weight, dietary and physical activity habits at 12 and 24 weeks after baseline by email. Afterwards, they will gain access to the standard online platform.

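### The SAP gives no method for participants who report no weight and no sensitivity analysis, although the sample size allows for 40% attrition; as written, the primary regression would use only those who report

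*SAP*

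**What the plan says.** The SAP is one paragraph. On who is analysed it says only "Analysis will be on an intention-to-treat basis". On the model it says "The models will be fitted using linear regression with weight as the outcome variable", with group and baseline weight as predictors, at each of the two visits. It continues: "Age, gender, dietary intake (kilocalories) and physical activity at baseline will enter the model for adjustment". Testing uses Hochberg's procedure with the "family wise error rate for each time point held at 2.5" per cent.

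The protocol, under Outcome measures, says "All outcomes will be assessed at baseline, 12 and 24 weeks afterwards" and "Weight and BMI change are the primary outcomes of the study and will be self-reported by the participants". Under Sample size it assumes "a 40% attrition rate, a sample size of 90 participants was calculated for each group". That is the only mention of attrition in either document, and it is tied to no visit and no arm. Under Randomization and allocation, "Participants were stratified by gender and category of body mass index".

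Neither document gives a missing-data assumption, an imputation rule, a model that uses both visits together, or a sensitivity analysis.

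**The concern.** Intention-to-treat fixes the arm in which a person is counted. It does not say what stands in for a weight that was never reported. Because the primary outcomes are self-reported, a person who stops reporting has no outcome. The random 10% sample under Quality Control checks the accuracy of self-report and is not described as recovering missing weights.

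A linear regression fitted separately at each visit will in practice drop rows with no weight at that visit. The SAP does not state this; it is an inference from the model. The people analysed would then be the reporters, not all those randomised. A person who reported at 12 weeks and then left would add nothing to the 24-week analysis, although that earlier weight is informative.

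At stake is whether the 24-week contrast estimates the effect in everyone randomised, and whether the rule for the missing part is settled before the data are seen. Contact differs by arm: Group 1 is invited by email to report, while Groups 2 and 3 have weekly platform content and Group 3 also has a weekly dietitian chat. Equal reporting across arms therefore cannot be taken for granted, although the documents give no direction for any imbalance.

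**Working it through.** **Inputs from the protocol (Sample size):** 90 per group, 40% attrition, 4 kg difference, SD 6, two-sided 0.05, power 90%. **From the SAP:** 2.5% family-wise at each visit.

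**1. The plan's own figure.** n = 2 × (1.960 + 1.282)² × 6² / 4² = 47.3, so 48 per group; 48 / 0.6 = 80 (82 with the t distribution). The stated 90 is not reproduced. I take 90 as given; nothing below depends on the difference.

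**2. Size of the missing part.** If the 40% applies at 24 weeks: 90 × 0.4 = 36 missing and 54 observed per arm, or 108 of 270 missing overall. If it does not, the split is unknown.

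**3. Error of the observed-case contrast, with no dropout mechanism assumed.** In one arm, full mean = 0.6 × observed + 0.4 × missing, so observed − full = 0.4 × (observed − missing). Between two arms, the error is 0.4 × (gap in arm A − gap in arm B). A 1 kg difference in gaps gives 0.4 kg; equal gaps give 0.

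**4. Different rules give different answers to the same data.** Assume 40% random dropout in each arm, a true 24-week difference of 4 kg, a week-12 difference of 2.7 kg, and half of dropouts seen at week 12.
- Observed cases, or a likelihood model using week 12: 4.0 kg.
- Last weight carried forward: 0.6 × 4 + 0.4 × (0.5 × 2.7 + 0.5 × 0) = 2.9 kg.
- Return to baseline: 0.6 × 4 = 2.4 kg.

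**5. Dropout tied to poor week-12 loss in one arm only, no true effect (illustration).** Let the chance of reporting be Φ(a + s·z), with z the standardised week-12 loss and 60% reporting overall. Then E[z | observed] = s/√(1+s²) × φ(0.253)/0.6, and bias = ρ × 6 × E. Here ρ is the assumed correlation (0.6 to 0.8) between week-12 and week-24 change, and 6 is read as the SD of 24-week change.

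| s | Lost at 1 SD below / above mean | E | Bias (kg) |
|---|---|---|---|
| 0.2 | 48% / 32% | 0.126 | 0.45–0.61 |
| 0.4 | 55% / 25% | 0.239 | 0.86–1.15 |
| 0.8 | 68% / 13% | 0.402 | 1.45–1.93 |

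This agrees with step 3: gaps of 3.6 to 4.8 kg in the last row, times 0.4.

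**6. The same dropout rule in both arms.** With no treatment effect the two biases cancel. They do not cancel when treatment works and dropout depends on kilograms lost at week 12. Take s = 0.8, a week-12 difference of 2.7 kg, week-12 SD 4.5 and 60% reporting across the two arms. Then 53% report in control and 67% in the active arm. E is 0.471 in control and 0.336 in active. Bias = ρ × 6 × (0.336 − 0.471), which is −0.49 kg at ρ = 0.6 and −0.65 kg at ρ = 0.8. The benefit is understated. At s = 0.4 the understatement is 0.17 to 0.23 kg.

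**7. What a model using week 12 leaves behind.** In simulation of the strongest case in step 5, a likelihood model that uses the 12-week weights leaves about 0.5 to 0.7 kg of bias if half of dropouts also missed week 12, and removes none if all did.

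**8. Timing.** Recruitment ran from 25 September to 24 October 2017. If follow-up began then, 12-week weights fell due from 18 December 2017 to 16 January 2018, and 24-week weights from 12 March to 10 April 2018. Both documents are dated 9 February 2018.

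**The case against.** **Intention-to-treat already defines the set.** This stands. The usual meaning is everyone randomised, analysed as allocated. A reader might infer that the plan has no analysis set at all; the text does not support that. The gap is narrower: how people in that set who have no weight enter the estimate.

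**ANCOVA at each visit is a standard analysis.** It is, and it is not itself the fault. With random dropout it is unbiased for the contrast.

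**The kilogram figures are assumptions.** They are. The slopes, the correlations, the share of dropouts seen at week 12 and the reading of SD 6 as the SD of change (the protocol calls it the SD of weight) are not in the documents, and the SAP's further covariates were left out. A reader might infer from step 5 that this trial is biased by up to 1.9 kg. Nothing in the documents favours that case over equal gaps. Only the 0.4 kg per 1 kg rule is free of an assumed mechanism.

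**Similar dropout in every arm would make the problem vanish.** Only in part. Step 6 shows that an identical rule gives about zero bias when there is no effect, but can understate a real one.

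**The sample was inflated for attrition, so power is protected.** With 54 per arm, power for 4 kg is 93% at 0.05 and 88% at 0.025. If Hochberg covers three pairwise contrasts (an assumption) and only one is significant, that one must reach 0.025 / 3 = 0.0083, where power is about 78%. Power is therefore not clearly secure. In any case, inflating the sample replaces lost numbers; it does not make reporters represent non-reporters.

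**Conclusion.** The concern holds as an omission with a concrete better alternative. The primary analysis claims intention-to-treat, but its only stated method would in practice analyse reporters alone and discard the 12-week information on later dropouts. No sensitivity analysis tests that choice. Up to 36 of 90 outcomes per arm are affected if the 40% allowance falls at 24 weeks.

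The error is 0.4 kg per 1 kg of difference in gaps at 40% missing, and the documents do not show whether the gaps differ. Under the strong shared-rule assumptions with a working treatment, the benefit is understated by about 0.5 to 0.65 kg. With one-arm dropout and no effect, the illustrations run from 0.45 to 1.93 kg. These show what the plan leaves unprotected; they do not predict this trial's result.

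The conclusion does not depend on power. Nor does it rest on the baseline-kilocalorie covariate, which the protocol describes calculating only for Groups 2 and 3. That conflict needs reconciling as a separate matter.

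**What to change.** - State that all randomised participants are included, as allocated.
- Make one named method primary in place of the observed-case regression: a repeated-measures model of the 12- and 24-week weights with baseline weight as covariate. Multiple imputation by arm that includes week-12 weight, followed by the planned ANCOVA, is an acceptable equivalent; the SAP should name one of the two.
- Add one named not-missing-at-random sensitivity analysis, such as delta-adjusted imputation over a stated range. This part is essential, because neither primary method corrects for people with no follow-up weight at all.
- Keep the observed-case ANCOVA as supportive.
- Report attrition by arm and by visit.
- Add BMI category to the model. It is the stratification factor the model lacks; gender is already there.
- Record when each rule was set. If follow-up began at recruitment, the 24-week rule could be fixed before those weights were due, but the 12-week rule should be declared as set after its weights were due.

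The cost is SAP wording and modest programming, with no new data. The real downside is that the sensitivity estimate may be less favourable than the observed-case one.

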Weight and height will be self-reported by the participants and BMI will be calculated by the formula weight in kg/ (height*height) in m². For the random 10% sample selected for additional measurements, weight will be measured in light clothing, without shoes on a Welmy ® analogic scale with stadiometer. For this sample, waist circumference will be measured at the mid-level between the last rib and the iliac crest using an inelastic tape and body composition will be measured by electrical bioimpedance using Sanny ® Bioimpedance.

Dietary intake and food-related behavior

For groups 2 and 3, calculation of the total daily caloric intake and dietary nutrients will be performed by an automatic dietary calculator which was based on food nutrition composition tables for the Brazilian population (<http://www.unicamp.br/nepa/taco/>).

Questions about the total number of daily serves of fruit and vegetables, and whole carbohydrates sources, as well as weekly serves of sweetened beverages and snack foods will be applied. Moreover, food-related behaviors, including number of days taking breakfast, number of daily meals, frequency of take-away food consumption and eating while watching television will be assessed by questionnaires.

Eating behavior

The random sample selected to anthropometry will have cognitive and behavioral components of eating assessed across three scales of cognitive restraint, uncontrolled eating and emotional eating by the Brazilian version of the Three Factor Eating Questionnaire-R21, (TFEQ-R21).

Physical activity and sedentary behavior

- The short-form of the International Physical Activity Questionnaire (IPAQ) will be used to estimate total MET-minutes/week and to classify participants into either high, medium or low physical activity categories according to the IPAQ Scoring Protocol [18].
- The daily screen-time (i.e., in front of TV, computers, video games, smartphones) and the daily sitting time will be used to assess sedentary behavior.
- Pedometers: the number of steps will be measured by XXX pedometer in the sample randomly selected to anthropometry.

Health perception

The Brazilian version of the *12-item Short-Form Health Survey – Version 2*, (QualityMetric Incorporated, Lincoln, RI, USA) which is a self-reported measure of health-related quality of life (HRQoL) designed to investigate multidimensional aspects

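### The primary model adjusts all three arms for baseline kilocalories, but the only kilocalorie source described covers Groups 2 and 3

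*SAP*

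**What the plan says.** The SAP specifies a linear regression of weight on treatment group and baseline weight at 12 and 24 weeks, analysed by intention to treat. It then adds: "Age, gender, dietary intake (kilocalories) and physical activity at baseline will enter the model for adjustment". It gives no rule for a missing covariate.

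The Protocol bears on this in several places:

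- **Dietary intake and food-related behavior.** The kilocalorie source is limited by arm: "For groups 2 and 3, calculation of the total daily caloric intake and dietary nutrients will be performed by an automatic dietary calculator". The next paragraph has no group limit and begins "Questions about the total number of daily serves of fruit and vegetables". It covers servings and eating habits, not kilocalories.
- **Interventions, Group 1.** "Access to the study website will be limited for the first 24 weeks". On reporting: "They will be invited to report their weight, dietary and physical activity habits at 12 and 24 weeks after baseline by email". Neither a baseline report nor kilocalories is mentioned there.
- **Interventions, Group 2.** The food diary belongs to the platform's self-monitoring area.
- **Outcome measures.** "All outcomes will be assessed at baseline, 12 and 24 weeks afterwards". Dietary habits are among these outcomes; kilocalories are not named. The section refers to Table 2 for detail, and that table is not in the available text.
- **Randomization and allocation.** "Once informed consent was obtained, participants were randomly allocated to one of the three groups". Participants were then told their group by automatic email.

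**The concern.** The trial asks whether the platform, with or without personalised feedback, does better than minimal intervention. The primary model needs a kilocalorie value for every participant, including controls, and the only described method of obtaining one excludes controls.

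If Group 1 has no values, the SAP's model cannot answer the trial's main question. The analyst would have to choose another primary model or an imputation method that the SAP does not specify, possibly after seeing outcome data.

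Timing is a second gap. Gender and BMI category are stratification factors and age is an eligibility criterion, so all were known before allocation. No passage says so for kilocalories or physical activity. Values recorded after participants learned their group could be affected by it, and adjusting for them could then distort the treatment comparison.

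**Working it through.** **Inputs.** From the Protocol's Sample size section: 90 per group, 40% attrition, difference 4 kg, SD 6.0, two-sided 0.05. From the SAP: the covariates, and Hochberg's procedure at 2.5% per time point. Expected completers per arm: 90 × 0.6 = 54, or 162 in all. The partial correlations used below are assumptions.

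**The plan's own figure.** The stated inputs give 48 per group, and 48 / 0.6 = 80, not 90. That is a separate matter; nothing below depends on it.

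**Step 1: can the model be fitted?** The columns are intercept, Group 2, Group 3, baseline weight, age, gender, kilocalories and physical activity, 8 in all. Suppose kilocalories are missing throughout Group 1.

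| Handling | Rows (after attrition) | Columns | Rank | Groups 2 vs 1 and 3 vs 1 | Group 3 vs 2 |
|---|---|---|---|---|---|
| Complete cases | 108 of 162 (0 controls) | 8 | 7 | not estimable | estimable |
| Complete cases, IPAQ in three categories | 108 of 162 | 9 | 8 | not estimable | estimable |
| Missing-value indicator | 162 | 9 | 8 | not estimable | estimable |
| Kilocalories removed | 162 | 7 | 7 | estimable | estimable |

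With no control rows, Group 2 + Group 3 equals the intercept column, so one column is redundant. With a missing-value indicator, that indicator is the Group 1 indicator, which equals intercept − Group 2 − Group 3. Before attrition the result is the same, with 180 of 270 rows in the complete-case fit.

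**Step 2: partial absence.** If only some controls have a value, the loss is in power. Unadjusted power for 4 kg at two-sided 0.05, with 54 in the active arm, is 93.4% with 54 controls, 80.7% with 27 and 60.4% with 14 (normal approximation).

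**Step 3: cost of removing kilocalories.** For partial correlation r with follow-up weight, the standard error rises by the factor 1/√(1 − r²):

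- r = 0.1: 1/√0.99, an increase of 0.5%
- r = 0.2: 1/√0.96, an increase of 2.1%
- r = 0.3: 1/√0.91, an increase of 4.8%

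Power uses the noncentral t with noncentrality 4 / (SD × √(2/54)). SD is 6.0 on 162 − 7 = 155 df without kilocalories, and 6.0 × √(1 − r²) on 154 df with kilocalories in all arms.

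| Two-sided level | Removed | Kept, r = 0.1 | Kept, r = 0.2 | Kept, r = 0.3 |
|---|---|---|---|---|
| 0.05 | 93.1% | 93.3% | 94.0% | 95.0% |
| 0.025/3 | 78.4% | 78.9% | 80.4% | 82.9% |

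The level 0.025/3 is Hochberg's strictest if three contrasts are tested, a number the SAP does not give. With two contrasts it is 0.0125, and power without kilocalories is 82.4%.

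**Step 4: filling Group 1 with the mean of Groups 2 and 3.** In 4,000 simulated trials (54 per arm, true effect −4 kg, kilocalories unaffected by allocation), the Group 2 versus 1 estimates were:

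| r | Method | Mean (kg) | Empirical SD | Coverage |
|---|---|---|---|---|
| 0.1 | Values in all arms | −4.00 | 1.183 | 94.5% |
| 0.1 | Removed | −4.00 | 1.189 | 94.4% |
| 0.1 | Mean filled | −4.00 | 1.188 | 94.4% |
| 0.3 | Values in all arms | −4.01 | 1.126 | 94.8% |
| 0.3 | Removed | −4.01 | 1.179 | 94.3% |
| 0.3 | Mean filled | −4.01 | 1.165 | 94.2% |

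Mean filling is unbiased under that assumption, but even at r = 0.3 it beats removal by only about 1% (1.179/1.165 = 1.012).

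**Step 5: dates.** Recruitment ran from 25 September to 24 October 2017; the SAP is dated 9 February 2018, 108 days (15.4 weeks) after it closed. If baseline was at enrolment, week 12 fell due between 18 December 2017 and 16 January 2018, so for everyone before the SAP date. Week 24 fell due between 12 March and 10 April 2018, so for no one.

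**The case against.** The strongest reply is that Group 1's values are not shown to be missing. The calculator sentence says how intake is obtained in Groups 2 and 3, not that controls have none. All outcomes are to be assessed at baseline, and everyone enrols online: "Interested participants can join the project online and create an account profile". The email sentence concerns weeks 12 and 24, so its silence on baseline is weak evidence; it also lists weight, which must exist at baseline for stratification. Group 1's website access is limited, not absent. Table 2 could list a dietary measure for all arms. One can read the documents as collecting intake from everyone at enrolment and then using the calculator in the platform arms.

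This stands as far as it goes: absence of data is unproven, and the zero control rows follow only if values are absent and incomplete rows are dropped. But none of these passages supplies a kilocalorie source for Group 1, and the one explicit source excludes it.

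Two further points have some force. Mean filling would rescue the control comparisons if kilocalories are unaffected by allocation; but the SAP does not specify it, and it gains almost nothing over removal. Removal could also discard a value recorded after allocation but before any intervention content. Since participants were emailed their group, leaving out a covariate not shown to precede allocation is still the standard course.

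**Conclusion.** The concern holds. The SAP and Protocol conflict as written: the primary model requires kilocalories in three arms, and the described source covers two. Followed literally with complete cases, the model retains no controls and cannot estimate either comparison with control. That outcome depends on Group 1 truly having no values, which the available text does not settle.

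This should be fixed; confidence is moderate, because the contradiction is clear and the state of the data is not. The cost of removal is small under the assumed correlations, and baseline weight stays in the model either way.

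**What to change.** Check the baseline records first: were kilocalories recorded in all three arms, and before allocation?

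- **If yes:** keep the covariate. Correct the Protocol's dietary intake section to name the source, arms and timing. Add to the SAP a rule for sporadic missing baseline values, for example the mean over all arms.
- **If no, or if it cannot be shown:** remove kilocalories from the primary model by a dated SAP amendment. State which 12-week and 24-week outcome data had been accessed by then; week 12 had probably fallen due for everyone when the SAP was dated, so an undocumented model change could look outcome-driven. Keep baseline weight, age and gender. Keep physical activity if it passes the same check of arms and timing. A dietary questionnaire item that passes that check may replace kilocalories.

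No new data are needed. The cost is one records check and one short correction or amendment. If kilocalories are removed, the price is the small loss of precision shown in the working.

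### The primary testing rule is valid, but gives up power that a Simes-gated closed test (three pairwise contrasts) or passing alpha between visits (two contrasts with control) would recover

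*SAP*

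**What the plan says.** The protocol's Design section describes three parallel arms: "This is a three-arm parallel randomized controlled trial". The SAP fits a linear model for weight, adjusted for baseline weight and other covariates, and states: "Analysis of covariance will be used to test for differences in weight loss between groups at each time point". Significance for the primary analysis rests on Hochberg's "multiple testing procedure with the family wise error rate for each time point held at 2.5" per cent.

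The SAP has no global test, no closed testing scheme and no rule for moving unused alpha from one visit to the other. It leaves three things open:

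- **Contrasts.** It does not list them. The wording fits all three pairwise contrasts, or only the two contrasts with control.
- **Sidedness.** It gives none for the 2.5%, although it does for the secondary tests.
- **BMI.** The protocol (Outcome measures) makes BMI change a primary outcome beside weight, but the SAP models weight only.

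**The concern.** With three arms, the three pairwise null hypotheses are logically linked: if any two equalities hold, so does the third. Once the hypothesis that all three arms are equal has been rejected, at most one pairwise null can still be true, and each pair can be tested at the full 2.5%. Hochberg ignores this link and still asks the middle p-value to meet 1.25% unless the largest meets 2.5%.

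Separately, when every comparison at one visit is significant, that visit's 2.5% has done its work. Under the SAP it is then discarded, although it could be used at the other visit without the trial-wide error exceeding 5%.

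What is at stake is power. The protocol (Sample size) was planned at two-sided 5% for a single difference, whereas the SAP tests several contrasts at 2.5% per visit.

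**Working it through.** **Inputs.** From the protocol (Sample size): 90 per group, 40% attrition, difference 4 kg, SD 6.0, power 90%, two-sided 5%. From the SAP: 2.5% per visit, two visits. Assumed: equal allocation (the block lengths of 3 and 6 suggest it), two-sided tests, SD 6 as the residual SD, and a between-visit correlation of 0.5 to 0.8.

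**The plan's own figure.** n = 2(1.960 + 1.282)² × 36/16 ≈ 47.3, so 48 completers per arm and 48/0.6 = 80 randomised (82 with a t-test). The stated 90 is not reproduced. I take 90 as given: 90 × 0.6 = 54 completers per arm.

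**Power of one 4 kg contrast.** The standard error is 6√(2/54) = 1.155, and 4/1.155 = 3.464.

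- At 5%: Φ(3.464 − 1.960) = 93.4%.
- At 2.5%: 88.9%.
- At 1.25%: 83.3%.
- At 2.5%/3 = 0.83%: 79.6%.

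**Error under the SAP rule.** 2.5% + 2.5% = 5%, so the rule is valid.

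**Three pairwise contrasts.** Order p1 ≤ p2 ≤ p3.

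- Hochberg rejects all three if p3 ≤ 0.025; failing that, the two smallest if p2 ≤ 0.0125; failing that, the smallest if p1 ≤ 0.0083.
- The Simes gate opens if p3 ≤ 0.025, or p2 ≤ 0.0167, or p1 ≤ 0.0083. Every pair with p ≤ 0.025 is then rejected.

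Each Hochberg condition opens the gate, and each pair that Hochberg rejects has p ≤ 0.025, so nothing is lost. Extra rejections arise, for example, when p1 ≤ 0.0083 and p2 lies between 0.0125 and 0.025. Simulation (1,000,000 trials per scenario, pooled t-tests on 159 df) found no lost Hochberg rejection:

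| True losses (kg) | Quantity | Hochberg | Simes-gated |
|---|---|---|---|
| 0/4/4 | each 4 kg contrast | 81.4% | 85.3% |
| 0/4/4 | both 4 kg contrasts | 72.4% | 79.9% |
| 0/4/4 | error on the equal pair | 1.9% | 2.5% |
| 0/3/4 | 3 kg contrast | 53.0% | 60.6% |
| 0/2/4 | 4 kg contrast | 79.2% | 80.0% |
| 0/2/4 | each 2 kg contrast | 22.9% | 29.2% |
| 0/4/8 | each 4 kg contrast | 88.2% | 88.4% |
| 0/0/0 | any rejection | 2.3% | 2.3–2.4% |

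Repeat runs differ by about 0.1 point.

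**An F-test gate is different.** Put one arm midway between two arms that are 3.12 kg apart. The outer pair has t = 3.12/1.155 = 2.70 and p = 0.0076, below 0.0083, so Hochberg rejects. The F-test gives p = 0.028, and the F-gated test rejects nothing.

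**Two contrasts with control.** Hochberg and the Simes-gated closed test then make identical decisions, so the gain is zero.

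**Passing alpha.** Rule: if every comparison at one visit is significant at 2.5%, test the other visit at 5%. Suppose a visit contains a true null. It can release its alpha only after a false rejection there, which its own 2.5% already counts. If it contains none, the other visit is tested at no more than 5%. Total error therefore stays within 5%.

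- Two contrasts with control, 4 kg at both visits: 87.1% to about 90% per contrast (89.7% to 90.5% over the assumed correlations).
- Same family, 4 kg at 12 weeks and 3 kg at 24 weeks: 59% to 68% for the 3 kg contrast.
- Same family, 4 kg at 12 weeks and no effect at 24 weeks: error at 24 weeks rises from about 2.4% to about 4% (3.6% to 4.2%).
- Three pairwise contrasts under Hochberg, 0/4/4 at both visits: power for both true contrasts changes by about 0.1 point, because release would need a false rejection. With 0/4/8, power for all three rises from 77% to 82–83%.

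**The case against.** The strongest reply is that nothing in the plan is wrong. Hochberg at 2.5% per visit is a recognised rule that holds total error at 5%, and choosing it is a choice among valid procedures. That stands.

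A reader might also infer more than the documents support:

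- **That any closed test beats Hochberg with three arms.** The F-gated version can lose a Hochberg rejection. The Simes-gated version gains only if all three pairwise contrasts are tested, which the SAP never says. If BMI belongs to the same family, a rule on three p-values does not fit.
- **That the two gains add up.** For 0/4/4 they belong to different families. Under three pairwise contrasts, passing alpha does almost nothing; under two contrasts with control, the closed test does nothing.
- **That the gain is general.** About 4 points on a 4 kg contrast appears when the two programme arms are truly equal. It is 0.8 points for 0/2/4 and about 0.2 for 0/4/8.
- **That power is below 90%.** This needs SD 6 to be the residual SD. The SAP adjusts for baseline weight and other covariates. At a residual SD of 5.4 (variance explained 1 − (5.4/6)² = 19%), plain Hochberg already gives 90.1% per 4 kg contrast under 0/4/4.

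Two costs are also real. Passing alpha means that one visit's error can exceed the 2.5% the SAP promises. Timing matters too: recruitment ended on 24 October 2017 and the SAP is dated 9 February 2018. If follow-up began at enrolment, which is not stated, the last 12-week reports were due about 16 January 2018. A more liberal primary rule adopted after results by arm were known would lack credibility.

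**Conclusion.** The point holds as a lost opportunity. The SAP's rule controls error, but for either plausible family a specific change can only add rejections, keeps trial-wide error at or below 5% and needs no assumption beyond Hochberg's own. With three pairwise contrasts the Simes-gated closed test gains about 4 points per 4 kg contrast and 7.5 points (79.9 − 72.4) for both when the programme arms are equal, and 1 point or less on a 4 kg contrast in the other patterns examined. With two contrasts with control, only alpha passing helps: about 3 points per 4 kg contrast, and about 9 points for a 3 kg effect at 24 weeks after 4 kg at 12 weeks. All figures rest on 54 completers per arm, two-sided tests and a residual SD of 6; the alpha-passing figures also rest on the assumed visit correlation. It is a free improvement and an optional refinement.

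**What to change.** 1. Name the primary contrasts, state that the 2.5% is two-sided, and say whether BMI belongs to the family.
2. If the family is the three pairwise weight contrasts, replace Hochberg with: *At each time point order the p-values p1 ≤ p2 ≤ p3. Proceed if p1 ≤ 0.0083, or p2 ≤ 0.0167, or p3 ≤ 0.025; then declare every pair with p ≤ 0.025 significant.* If it is two contrasts with control, keep Hochberg.
3. In either case add: *If all comparisons at one time point are significant, the other time point is tested by the same rule at 5%.* In the three-contrast rule the limits then become 0.0167, 0.0333 and 0.05.
4. State that total error is held at 5% and that error at a single visit may then exceed 2.5% (about 4% in simulation).

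The cost is a few SAP sentences and a few lines of code, with no extra participants and no choice of a main time point. The price is the looser limit at a single visit. Adopt the change only before outcome data by arm have been seen, and record the date; otherwise keep the existing rule.
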